8.6 Prohibitions and Restrictions

The most important required restriction for study participants is pregnancy.

Imaging is performed ambulatory. After imaging, participant may go back home or go back to work without any particular precautions.

Any concomitant medication deemed necessary for the welfare of the participant during the study may be given at the discretion of the Investigator. However, it is the responsibility of the Investigator to ensure that details regarding the medication are recorded in full in the case report form, including any changes that have occurred during the study.

9. Investigational Product, Dose and Mode of Administration

The full name of the Investigational Drug is “Kit for the Preparation of Tc-99m Recombinant Human Annexin V-128 for Injection”.

9.1 Description of Investigational Product

The kit will be prepared, packaged and released according to the manufacturer’s Standard Operating Procedures (SOPs), and in compliance with the principles of the Good Manufacturing Practice (GMP) guidelines, ICH Good Clinical Practice (GCP) guidelines, and applicable local laws/regulations.

The investigational product will be supplied as a sterile, single vial lyophilised kit for reconstitution at the clinical site with ^{99m}Tc solution eluted from a generator.

A single dose vial contains 0.4 mg of rhAnnexin V-128. The kit contains also stannous chloride (reducing agent), sodium α-D-Glucoheptonatedihydrate (transchelating agent), gentisic acid sodium salt hydrate (radiation stability enhancer), hydroxypropyl-β-cyclodextrin (solubilizing

agent), sodium metabisulfite (antioxidant) and trehalosedihydrate (lyoprotectant and cake forming agent). Lactic acid is also present as buffering agent. The kit composition details are included in the Appendix II.

9.2 Handling, Preparation and Storage

The investigational product must be stored, handled and administered only by qualified/authorized personnel and must be prepared in accordance with pharmaceutical quality requirements, and radiation safety regulations. ^{99m}Tc-rhAnnexin V-128 must be administered at the investigational site. Based on the stability tests performed (Appendix I), the Annexin Kit can be stored upon receipt at 5°C ± 3°C until the expiry date stated on the labels.

A single dose vial containing 0.4 mg of lyophilized rhAnnexin V-128, will be reconstituted with 2 mL ± 0.2 mL containing 740 MBq ± 74 MBq (20 mCi ± 2 mCi) of ^{99m}Tc eluted from the generator. Development studies have shown that this amount of radioactivity provides a sufficient amount of radioactivity for QC testing and the foreseen ^{99m}Tc rhAnnexin V-128 dose of 350 MBq up to 4 h after labeling. The administration volume (corresponding to 350 MBq) is calculated according to the estimated time of injection, on the basis of the physical decay of the radionuclide (half-life = 6.02 h). Stability studies performed on the Drug Product have demonstrated radiochemical purity at 6 h from labeling greater than 90%, which is in line with current specifications of the Kit for the preparation of ^{99m}Tc-rhAnnexin V-128 for injection. For the purpose of this study, it is recommended to administer the reconstituted solution within 4 hours after completion of the radiolabeling. It is also required to determine the amount of radioactivity injected to the patient by measuring the radioactivity before and after injection with an appropriate radioactivity calibration system.

The labeling reaction requires 90 minutes and the reconstituted radiolabeled product is stable for 6 hours. Technetium-99m eluate should be obtained from an approved commercial Mo-99/Tc-99m generator that has been eluted within the past 24 hrs. The radiopharmacy will be directed to use the eluate within one hour of milking the generator.

9.3 Investigational Product Accountability

Drug inventory and accountability records for the “Kits for preparation of Technetium ^{99m}Tc-rhAnnexin V-128 for injection” will be kept by the Investigator/radiopharmacist, and must be documented throughout the study.

On an ongoing basis, the Investigator/radiopharmacist will conduct an investigational product (IP) supply inventory and to record the results of this inventory on the IP Accountability Record to reconcile delivery records with those of used and unused product. Any discrepancies must be accounted for. Appropriate forms of deliveries and returns must be signed by the person responsible for drug accountability. Used/unused “Kits for preparation of Technetium ^{99m}Tc-rhAnnexin V-128 for injection” will be locally discarded.

Refer to Appendix II for detailed instruction on the Radiolabeled Imaging Product ^{99m}Tc-rhAnnexin V-128, Cautionary notes, Analytical and Biological Controls, Stability and Shelf Life.

9.4 Investigational Product Dose, Mode of Administration

The "Kit for preparation of ^{99m}Tc -rhAnnexin V-128 for injection" consists of 1 dose.

Participants will receive one dose of $350 \text{ MBq} \pm 10\%$ of ^{99m}Tc -rhAnnexin V-128 administered as a single intravenous bolus.

10. Study Procedures

Voluntary written informed consent will be obtained prior to the initiation of any study-related procedures. Study conduct procedures will include a screening visit, the imaging studies, a phone visit within 24 hour post ^{99m}Tc -rhAnnexin V-128 administration visit and a visit at 30 days.

10.1 Baseline Assessments

- Each participant's date of birth (mm/yyyy), gender, ethnicity, weight, height, medical history, and relevant baseline characteristics will be recorded.
- Results from any standard of care testing related to the participant's condition will be collected.
- Women of childbearing potential must have negative pregnancy test at screening and before the investigational product administration.
- Limited physical exam (height, weight, BMI) and vital signs (systolic and diastolic blood pressure, heart rate), will be recorded.

10.2 Laboratory Assessments

Blood samples for hematology, biochemistry and urinalysis will be obtained at baseline for screening, 30 +/- 3 days post IP administration and following any adverse events.

In case of clinically significant abnormalities in baseline laboratory values, the participant will be declared as a screening failure.

Study Protocol

Hematology	Coagulation	Blood Chemistry	Urinalysis

 • WBC with differential • RBC • Platelets • Hb • MCV • Hematocrit 	
 • PT • PTT • INR 	
 • BUN • Uric acid • Albumin • Direct bilirubin • LDH • Calcium • Chloride • Phosphorus • Total cholesterol • Total protein • Serum creatinine • Total bilirubin • AP • AST/ASAT • ALT/ALAT • Gamma-GT • Sodium • Potassium • Glucose • β-HCG at screening 	
 • Dipstick test¹ • Pregnancy test (before injection of study product, if applicable)

¹ In case one of the assessments of the dipstick test is positive, a microscopic analysis of the urine must be performed.

Laboratory Assessments will be performed by the [REDACTED] [REDACTED] The Ottawa Hospital according to Ministry of Health and Long Term Care (MHLTC) standards.

10.3 ^{99m}Tc-rhAnnexin V-128 Planar and SPECT Imaging of the Carotid Arteries and Aorta and Image Analysis

Planar and SPECT imaging of the carotids and aorta will be performed 60 and 120 minutes after injection of tracer.

Administration of the ^{99m}Tc-rhAnnexin V-128 (350 MBq \pm 10 %) will be as a single bolus via an intravenous catheter in an antecubital vein followed by a saline flush. Negative pregnancy test for women of childbearing potential will be confirmed on the day of administration.

All images will be acquired with a dual head SPECT/CT gamma camera with low-energy high-resolution collimators. The energy acceptance window for the ^{99m}Tc photopeak will be 140 keV (+/- 10%). A low dose CT scan (helical, 120 kVp, 1 mA with 1.9 pitch) will be acquired of the neck, thorax and abdomen for attenuation correction.

Study Protocol

Reconstruction will be done using iterative reconstruction incorporating CT-based attenuation correction and dual-energy-window scatter correction. Planar and SPECT images of the carotid arteries and thoracic and abdominal aorta will be acquired at 1 and 2 hours post-injection. Acquired images will be stored for off-line analysis using a Hermes Gold workstation (Hermes Medical Solutions). Volumes-of-interest (VOIs) will be placed over the carotids and the thoracic and abdominal aortic sections to determine image counts from the attenuation and scatter corrected images. A ^{99m}Tc source of known activity will be imaged and used to determine the imaging system calibration factor for converting reconstructed image counts into an activity concentration (MBq/cc or % injected dose/gram).

A normal database of carotid and aortic uptake will be determined from 10 control participants and used to identify abnormal uptake in carotid artery disease participants.

Inter and intra-observer variability will be determined by repeated analysis of the images of 20 participants. Two observers will carry out the assessment of inter-observer variability. Images will be anonymized prior to analysis and observers will be blinded to all clinical data.

10.4 ^{99m}Tc -rhAnnexin V-128 Radiation Risk Assessment

Participants will receive radiation from 1) ^{99m}Tc -rhAnnexin V-128 (350 MBq) for a dose of 2.2 mSv (7.7 ± 0.8 uSv/MBq) and 2) the CT scan for attenuation correction for a dose of 1.8 mSv. Total dose for ^{99m}Tc -rhAnnexin V-128 and CT components will be 4.0 mSv.

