Study design and Methodology	
This is a single-centre, single dose, PoC, Phase II study. Participants who have signed the informed consent and are eligible to participate in the study will undergo the following assessments:
 
 • A screening visit will be conducted within 8 weeks ^{99m}Tc-rhAnnexin V-128 imaging. Eligible and consenting participants will undergo a limited physical examination (height, weight, BMI), vital signs (systolic and diastolic blood pressure, heart rate), blood analysis and urinalysis. The following blood analysis will be conducted: CBC with automated differential, general chemistry panel (SMA-20) including, PT/PTT, INR (international normalized ratio for PT values) and assessment of anti-annexin V-128 antibodies. • Carotid ultrasound will be carried out within 8 weeks prior to the ^{99m}Tc-rhAnnexin V-128 planar and SPECT/CT imaging. Imaging visit: planar and dedicated SPECT/CT imaging of the carotids and aorta will be done 60 minutes after injection of tracer, and 120 minutes after injection. Vital signs assessment/participant monitoring will be done throughout the visit. • Within 24 hours after the administration of ^{99m}Tc-rhAnnexin V-128, participants will be called for the assessment of possible adverse events. • 30 +/- 3 days post ^{99m}Tc-rhAnnexin V-128 injection, all participants will return to clinic for a final blood sampling to rule out the development of anti-annexin V-128 antibodies. The following blood analysis will also be conducted: CBC with automated differential, general chemistry panel (SMA-20) including, PT/PTT, and INR. • Once the first 15 patients and 5 normals have been administered with ^{99m}Tc-rhAnnexin V-128 and have performed the imaging visits, the Data Monitoring Committee will review the images. The visual assessment of the scans in these first 20 participants will support the continuation or the termination of the Phase II study.
Treatment	After reconstitution and radiolabeling, ^{99m}Tc -rhAnnexin V-128 is administered as a single intravenous bolus of 350 MBq +/- 10% at the imaging visit (Day 0).
Inclusion/exclusion criteria	
Inclusion criteria
 
For all participants:
 
 1. Males and females age 18 years or greater 2. Able and willing to comply with the study procedures 3. Negative pregnancy test for women of childbearing potential at screening and on the day of administration of ^{99m}Tc-rhAnnexin V-128.

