^{99m}Tc labeled rhAnnexin V-128 has been evaluated in a Phase I clinical trial at the University of Ottawa Heart Institute in 12 normal volunteers. No significant adverse effects were observed. Blood clearance was rapid. Greatest radiotracer uptake was in the kidneys, bladder (due to rapid kidney clearance), liver and lungs. Total effective dose (IRCP 60) for ^{99m}Tc labeled rhAnnexin V-128 was 7.7 + 0.8 uSv/MBq and was significantly less than 11.0 + 0.8 uSv/MBq reported for ^{99m}Tc-HYNIC-Annexin V-128²⁸.

Ultrasound imaging can provide further insight into the morphology of plaque. B-mode ultrasound derived measures of plaque echogenicity can predict the content of soft lipid tissue and the amount of calcification in carotid plaque^{29, 30}. Echogenic plaque is typically composed of fibrous tissue and calcification, while echolucent plaque is lipid-rich^{29, 30}. Plaque morphology by ultrasound has predictive value for identifying patients at increased risk of ischemic cerebrovascular events independent of degree of stenosis and vascular risk factors³¹. A recent review of ultrasound, computed tomography and magnetic resonance imaging of the carotid arteries concluded that ultrasound was preferable at the present time due to high spatial and temporal resolution, safety, low cost and wide availability³².

The goal of the present investigation is to assess the feasibility of ^{99m}Tc-rhAnnexin V-128 planar and SPECT imaging as a technique for detection of apoptotic carotid plaque in asymptomatic patients with significant carotid artery disease. This investigation will determine the prevalence of significant apoptotic activity in carotid plaque in patients with carotid disease. ^{99m}Tc-rhAnnexin V-128 uptake in the carotid arteries as a measure of apoptotic activity will be compared to plaque ultrasound-based echogenicity and echolucency, measures of plaque vulnerability. Aortic uptake of ^{99m}Tc-rhAnnexin V-128 will be imaged and related to carotid uptake of ^{99m}Tc-rhAnnexin V-128.

4. Study Objectives

The primary objective of this investigation is:

- To determine the feasibility of imaging apoptotic activity in carotid atherosclerotic plaques of asymptomatic or previous symptomatic with TIA only patients with significant carotid artery disease by using ^{99m}Tc-rhAnnexin V-128 imaging and to report the prevalence of abnormal ^{99m}Tc-rhAnnexin V-128 scans.

The secondary objectives are:

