Reconstruction will be done using iterative reconstruction incorporating CT-based attenuation correction and dual-energy-window scatter correction. SPECT images of the carotid arteries and thoracic and abdominal aorta will be acquired at 1 and 2 hours post-injection. Acquired images will be stored for off-line analysis using a Hermes Gold workstation (Hermes Medical Solutions). Volumes-of-interest (VOIs) will be placed over the carotids and the thoracic and abdominal aortic sections to determine image counts from the attenuation and scatter corrected images. A ^{99m}Tc source of known activity will be imaged and used to determine the imaging system calibration factor for converting reconstructed image counts into an activity concentration (MBq/cc or % injected dose/gram).

A normal database of carotid and aortic uptake will be determined from 10 control participants and used to identify abnormal uptake in carotid artery disease participants.

Inter and intra-observer variability will be determined by repeated analysis of the images of 20 participants. Two observers will carry out the assessment of inter-observer variability. Images will be anonymized prior to analysis and observers will be blinded to all clinical data.

4.3.3.4 99mTc-rhAnnexin V-128 Radiation Risk Assessment

Participants will receive radiation from 1) ^{99m}Tc-rhAnnexin V-128 (350 MBq) for a dose of 2.2 mSv (7.7 ± 0.8 uSv/MBq) and 2) the CT scan for attenuation correction for a dose of 1.8 mSv. Total dose for ^{99m}Tc-rhAnnexin V-128 and CT components will be 4.0 mSv.

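### The radiation risk statement gives 2.2 mSv for the tracer, but its own activity and dose coefficient multiply to 2.7 mSv, so the 4.0 mSv total should be about 4.5 mSv

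*Protocol*

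**What the plan says.** Protocol section 10.4 sets out the radiation exposure in two parts. The tracer part gives 350 MBq "for a dose of 2.2 mSv (7.7 ± 0.8 uSv/MBq"). The second part is "the CT scan for attenuation correction for a dose of 1.8 mSv". Their sum is given as 4.0 mSv.

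SAP section 4.3.3.4 carries the same figures, ending with "CT components will be 4.0 mSv".

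Both tracer inputs appear elsewhere in the protocol:

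- **Coefficient.** Section 3 (Background and Rationale) reports the Phase I result in 12 normal volunteers: the effective dose "was 7.7 + 0.8 uSv/MBq and was significantly less than" the value for the older annexin tracer.
- **Activity.** The Treatment row of the synopsis says the product is "administered as a single intravenous bolus of 350 MBq +/- 10% at the imaging visit (Day 0"). Sections 6, 9.4 and 10.3 give the same 350 MBq ± 10%.

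**The concern.** Effective dose is administered activity multiplied by the dose coefficient. Section 10.4 prints the activity, the coefficient and the result in one sentence, and the result is not the product of the other two. The three figures cannot all be right.

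The discrepancy runs in the unfavourable direction: if the activity and coefficient are correct, participants receive more than the protocol says. Section 10.4 is the protocol's radiation risk statement for everyone enrolled, including ten controls whom section 8.3 describes as healthy volunteers. Sections 8 and 15.2.2 send the protocol to the research ethics board and Health Canada for approval. An exposure figure that is too low would misinform that review, along with any consent wording taken from it.

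**Working it through.** **Inputs**

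| Quantity | Value | Source |
|---|---|---|
| Activity, nominal | 350 MBq | Protocol 10.4 |
| Activity, permitted range | ± 10%, i.e. 315 to 385 MBq | Protocol synopsis, 6, 9.4, 10.3 |
| Dose coefficient | 7.7 ± 0.8 uSv/MBq, i.e. 6.9 to 8.5 | Protocol 10.4; same value in section 3 |
| CT dose | 1.8 mSv | Protocol 10.4 |
| Stated tracer dose | 2.2 mSv | Protocol 10.4; SAP 4.3.3.4 |
| Stated total | 4.0 mSv | Protocol 10.4; SAP 4.3.3.4 |

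**Step 1: the stated total.** 2.2 + 1.8 = 4.0 mSv. The sum is correct, so 2.2 is the figure the authors used and not a misread digit.

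**Step 2: the stated tracer dose.** Dose (mSv) = activity (MBq) × coefficient (uSv/MBq) ÷ 1000.

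350 × 7.7 ÷ 1000 = 2.695 mSv, about 2.7 mSv. The stated 2.2 mSv is not reproduced.

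**Step 3: the total on the plan's inputs.** 2.695 + 1.8 = 4.495 mSv, about 4.5 mSv.

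**Step 4: size of the gap.** 2.695 − 2.2 = 0.495 mSv. As a share of the tracer dose, 0.495 ÷ 2.695 = 18%. As a share of the total, 0.495 ÷ 4.495 = 11%.

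**Step 5: whether a tolerance explains it.**

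| Activity (MBq) | Coefficient (uSv/MBq) | Tracer (mSv) | With 1.8 mSv CT (mSv) |
|---|---|---|---|
| 315 | 7.7 | 2.43 | 4.23 |
| 385 | 7.7 | 2.96 | 4.76 |
| 350 | 6.9 | 2.42 | 4.22 |
| 350 | 8.5 | 2.98 | 4.78 |
| 315 | 6.9 | 2.17 | 3.97 |
| 385 | 8.5 | 3.27 | 5.07 |

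Varying either input alone gives 2.4 to 3.0 mSv, which excludes 2.2. Only the lowest activity combined with the lowest coefficient rounds to 2.2 mSv.

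**Step 6: what 2.2 mSv would require.** At 7.7 uSv/MBq, the activity would be 2200 ÷ 7.7 = 286 MBq. At 350 MBq, the coefficient would be 2200 ÷ 350 = 6.29 uSv/MBq. Neither value appears in the documents.

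**The case against.** The arithmetic is not open to dispute. The case on the other side concerns how much it matters and how far the claim may go.

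- **Importance.** The error sits in one descriptive statement. It touches no endpoint, eligibility rule, administered activity, stopping rule or analysis. The gap is 0.5 mSv, and the documents name no dose limit that 4.5 mSv would cross and 4.0 mSv would not. A reader can also recompute the figure from the same sentence. All of this stands, and it limits the consequence. It does not make the figure acceptable in a risk statement submitted for approval.
- **The range.** At the joint lower extreme the dose is 2.17 mSv, which rounds to the stated value. This stands as a qualification: 2.2 mSv falls outside the permitted activity range at the stated coefficient, but not outside every combination of the two tolerances. It does not rescue the statement, because section 10.4 ties 2.2 mSv to 350 MBq and offers it as the expected dose, not as a minimum. The matching upper extreme is 3.3 mSv.
- **Which figure is wrong.** The documents do not say where 2.2 came from, so strictly only an inconsistency is proven. Understatement is the likelier reading, because the activity and the coefficient are both confirmed elsewhere in the protocol.
- **Consent wording.** The consent form was not available, so any effect on it is conditional.
- **The SAP.** Its section 4 is a transcription of the protocol. The repeat there is a copy, not a second error.

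**Conclusion.** The concern holds. On the plan's own activity and coefficient, the tracer dose is about 2.7 mSv, not 2.2, and the total is about 4.5 mSv, not 4.0. The stated values are low by 0.5 mSv: 18% of the tracer dose and 11% of the total.

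This rests on three assumptions: that 350 MBq and 7.7 uSv/MBq are the intended inputs, that 1.8 mSv is correct for CT, and that 1.8 mSv covers all the CT acquired. The last is not fully settled. The synopsis describes SPECT/CT at both 60 and 120 minutes. Protocol 10.3 refers to a single low-dose CT, and SAP Listing 16.2.6.1 and Table 14.2.1.2 label only the 120-minute scan as SPECT/CT. The tracer finding does not depend on the answer.

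No statistical result is affected. The statement is nonetheless wrong as written and should be corrected.

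**What to change.** Reconcile activity, coefficient and effective dose in Protocol 10.4, and carry the result into SAP 4.3.3.4.

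- If 350 MBq and 7.7 uSv/MBq stand, give the tracer dose as about 2.7 mSv, with 2.4 to 3.0 mSv over the permitted ± 10% on activity. Give the total as about 4.5 mSv, or 4.2 to 4.8 mSv over the same range.
- If 2.2 mSv is the intended figure, correct the activity or the coefficient wherever it appears, with its source.
- State how many CT acquisitions the 1.8 mSv covers.
- Check any participant information that quotes a dose, and correct it to match.

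The cost is a few changed numbers in two documents and a check of the consent text, with whatever ethics or regulatory notification the change requires under Protocol 15.5. The stated exposure becomes slightly less favourable. If the activity stands, study conduct does not change.

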10.5 Ultrasound Examination

Clinical evidence of 50% or more carotid stenosis in one or more carotid arteries on carotid ultrasound within 10 years prior to enrolment is required for inclusion in the trial.

Evidence of 50% or more carotid stenosis has to be confirmed in a more recent US imaging within 8 weeks prior to ^{99m}Tc -rhAnnexin V-128 administration. If not confirmed, the participant will be declared as a screening failure.

B-mode and color Doppler ultrasound studies will be acquired of both carotid arteries and performed with an ultrasound scanner equipped with a 5- to 7-MHz transducer. Plaque morphology, as echogenicity, defined as reflectance of the emitted ultrasound signal, will be assessed as previously described²⁹ and graded from 1 to 4 as echolucent, predominantly echolucent, predominantly echogenic, or echogenic. The vessel lumen will be used as the reference structure for defining echolucency, and the bright echo zone produced by the media-adventitia interface in the far wall will be used as the reference structure for defining echogenicity. Interobserver reproducibility of plaque morphology in stenotic arteries has been previously assessed ($\kappa=0.56$, 95% CI 0.38 to 0.74)³¹.

The degree of stenosis will be calculated by the following equation: $(1 - \text{PSV}_r / \text{PSV}_s) \times 100\%$, where PSV_r denotes peak systolic velocity at the point of reference (here, the distal carotid artery) and PSV_s the peak systolic velocity in the stenosis³¹.

11. Data Monitoring Committee

The Data Monitoring Committee (DMC) consists of investigators and Sponsor representatives, as well as external persons such as independent experts, if deemed necessary by the Sponsor. The DMC will review and evaluate the images of the first 15 patients and the first 5 healthy participants in terms of image quality, carotid target uptake and clinical relevance of the study product. The DMC will also review the safety data. The frequency of abnormal carotid scans will be determined in the participant and normal groups. The study will be terminated if there is a low frequency of positive scans in the carotid participant group or high frequency of positive scans in the normal group.

The DMC will promptly give recommendations to continue or terminate the study. The DMC report will be prepared by the Sponsor and sent to the REB and regulatory authorities as required. Preliminary results can be used by the Sponsor for publication purpose, before the end of the main trial.

12. Statistical methods

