12.4 Efficacy

Primary endpoint of PoC:

The feasibility of imaging apoptotic activity in carotid atherosclerotic plaques using ^{99m}Tc-rhAnnexin V-128 will be determined by the data monitoring committee (visual image review and consensus).

Primary endpoint of Phase II:

Efficacy of ^{99m}Tc-rhAnnexin V-128 planar and SPECT/CT imaging will also be evaluated by determining the prevalence of abnormal ^{99m}Tc-rhAnnexin V-128 scans.

Secondary endpoints:

Descriptive statistics of ^{99m}Tc-rhAnnexin V-128 uptake in control subjects will be presented by areas of interest to assess the background uptake profile.

^{99m}Tc-rhAnnexin V-128 uptake will be related to ultrasound data of plaque echogenicity and echolucency, by direct comparison and by using correlation test and/or diagnostic test performance methods (McNemar test) if appropriate.

^{99m}Tc-rhAnnexin V-128 uptake in carotids will be correlated to its aortic uptake in all participants.

Efficacy analysis of the primary endpoint will be mainly descriptive in nature. Inferential statistics (such as comparisons, correlations...) will be mainly conducted as explorative analyses to serve as the basis for future confirmatory trials.

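### Neither document states that the DMC's visual read of the 15 patient and 5 control scans, which is the PoC primary endpoint, is masked to group

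*Protocol*

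**What the plan says.** Protocol 12.4 and SAP 6.1.2.1 make the PoC primary endpoint a committee judgement reached by "visual image review and consensus". Protocol section 11, repeated in SAP 6.1.16, says the committee "consists of investigators and Sponsor representatives, as well as external persons such as independent experts, if deemed necessary by the Sponsor". Its task is to "review and evaluate the images of the first 15 patients and the first 5 healthy participants in terms of image quality", carotid uptake and clinical relevance. It also reviews the safety data.

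Section 11 then sets up a contrast between groups: "The frequency of abnormal carotid scans will be determined in the participant and normal groups". The consequence follows: "The study will be terminated if there is a low frequency of positive scans in the carotid participant group", or if positive scans are frequent in the normal group. Neither document puts a number on low or high. SAP 6.1.2.1 adds that a scan is called positive or negative from the number, location, length and uptake grade of each plaque.

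The one statement about masking is in protocol 10.3 and SAP 4.3.3.3: "Images will be anonymized prior to analysis and observers will be blinded to all clinical data". It ends the paragraph on inter- and intra-observer variability, where two observers repeat the analysis of 20 participants' images. SAP 6.1.2.1 cites a DMC charter, but only as the place where the committee's outputs are defined.

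**The concern.** The read is subjective, and the quantity that matters is a difference between two groups. Under the plan as written, a reader may know which scans come from people with at least 50% stenosis and which from healthy volunteers without carotid atherosclerosis. Grading uptake plaque by plaque is especially open to that knowledge, because the reader knows beforehand whether there should be a plaque to find.

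The likely bias runs one way in each group: borderline patient scans are called positive and borderline control scans negative. That is the pattern that lets the study continue and supports the feasibility claim. Protocol section 11 also lets the sponsor, which prepares the DMC report, publish preliminary results before the main trial ends. An unmasked PoC result could therefore stand on its own in the literature.

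**Working it through.** **Is masking stated anywhere for this read?** The places that describe the DMC review are the protocol synopsis, protocol 11, 12.4, 13.5 and 14, and SAP 4.3.4, 6.1.2.1, 6.1.15 and 6.1.16. None mentions coded scans, mixed order, or withholding group or ultrasound results. The blinding sentence in protocol 10.3 and SAP 4.3.3.3 refers to observers, directly after two observers have been introduced for the variability exercise. A committee consensus read is a different activity, and the sentence is not extended to it. It could still be read as covering all image analysis. Masking of the DMC read is therefore not stated, which is weaker than saying it is absent.

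**Could group become known by another route?** The same committee reviews safety data, and SAP 6.1.3.1 summarises adverse events by patients versus controls. Neither document orders the scan reading before the safety review.

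**How much could reader knowledge matter?** The plan gives no operating characteristics for the 15 + 5 step, so there is no figure to reproduce. The following is an illustration, and every setting in it is assumed.

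- Continue if at least 5 of 15 patients and at most 1 of 5 controls are positive.
- The true positive rate p is the same in both groups, so the tracer does not discriminate.
- Knowledge of group turns a share b of negative patient scans positive and the same share b of positive control scans negative.

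The read rates are: patients p + (1 − p)b; controls p(1 − b).

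P(continue) = P(X ≥ 5), X ~ Bin(15, patient rate), multiplied by P(Y ≤ 1), Y ~ Bin(5, control rate).

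For p = 0.2:

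| b | patient rate | control rate | P(X ≥ 5) | P(Y ≤ 1) | P(continue) |
|---|---|---|---|---|---|
| 0 | 0.20 | 0.20 | 0.164 | 0.737 | 0.12 |
| 0.1 | 0.28 | 0.18 | 0.415 | 0.778 | 0.32 |
| 0.2 | 0.36 | 0.16 | 0.678 | 0.817 | 0.55 |
| 0.3 | 0.44 | 0.14 | 0.863 | 0.853 | 0.74 |

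Over the same range of b, P(continue) goes from 0.01 to 0.68 for p = 0.1 and from 0.26 to 0.68 for p = 0.3. The direction is the same for each p, while the size depends heavily on p and b.

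**Would the control group expose such a shift?** No. The exact 95% interval is 0 to 0.52 for 0/5 positive controls and 0.005 to 0.72 for 1/5.

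**The case against.** The strongest reply is that silence about the DMC does not show an unmasked read. The blinding sentence sits in the image-analysis section and is not expressly limited to the variability exercise. Participant identifiers (protocol 8.4) carry no group code, and the charter or the DMC assessment form may already set reading order and masking. This stands, and it is why the point concerns what is not stated.

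The consequence is also bounded. Under protocol sections 11 and 14 the committee recommends and the sponsor may discontinue, and the review also covers image quality, clinical relevance and safety. Protocol 12.4 calls the efficacy analysis mainly descriptive. This limits the weight of the point but leaves the PoC primary endpoint exposed.

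Three stronger readings are tempting and are not supported:

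- **The staff who enrolled participants read their scans.** The documents say only that investigators sit on the committee, and independent experts may be added. In a single-centre study, knowledge of group is plausible, but it is an inference.
- **The final prevalence result rests on the committee's impressions.** SAP 6.1.2.2 defines the Phase II endpoint by comparing measured activity concentration with the normal database. The SAP listings index does tie Listing 16.2.6.2 to the DMC form, but its template holds numeric target-to-background ratios supplied by the sponsor. Positive and negative results are in Listing 16.2.6.1.
- **Small-sample granularity measures the bias.** One changed read moves the frequency by 1/15 = 6.7 points in patients and 1/5 = 20 points in controls. At an assumed 10% false-positive rate, at least one of five controls is positive with probability 1 − 0.9^5 = 41%. These figures would be the same under a fully masked read.

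**Conclusion.** The point holds as a gap in the stated method. A subjective consensus read that serves as the PoC primary endpoint and informs continuation has no stated masking to group, and the only blinding sentence does not clearly reach it. Followed as written, the plan permits an unmasked read whose likely bias favours continuation and the feasibility claim. The Phase II prevalence, as SAP 6.1.2.2 defines it, is less directly affected.

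The size of any bias cannot be derived from the documents. The rise from about 12% to 32% and 55% depends on the assumed cut-offs, a common true rate of 0.2, and shifts of 10% and 20%. It shows that modest shifts could matter, and does not estimate what happened or will happen. If the charter already requires a masked read, only a cross-reference is missing. This should be corrected, with medium confidence because the charter has not been seen.

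**What to change.** In protocol section 11 and SAP 6.1.2.1 and 6.1.16, require that:

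- the 20 scans are presented to the DMC under a code, in one random order that mixes patients and controls;
- group, ultrasound findings and other clinical data are withheld until each positive or negative call and each grade is recorded and locked;
- results are tabulated by group, and safety data released to the committee, only after that lock.

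State also whether the blinding sentence in protocol 10.3 and SAP 4.3.3.3 covers the DMC read. If the charter already contains these rules, cite it for them. If the scans have already been read, report whether the readers were masked and have the coded set re-read.

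The cost is a coding list and a reading order, with no extra readers or participants and no change to the sample size. One limit remains: the low-dose CT may partly reveal disease even on a coded scan, so masking would be incomplete, and the report should say so.
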